4 REGISTRATION PROCEDURES

4.1 GENERAL GUIDELINES

Eligible patients will be entered on study centrally at the CCR by the Study Coordinator.

Issues that would cause treatment delays should be discussed with the Principal Investigator.

Except in very unusual circumstances, each participating institution will order DCTD-supplied agents directly from CTEP. Agents may be ordered by a participating site only after the initial IRB approval for the site has been forwarded by the Coordinating Center to the CTEP PIO ([contact]) except for Group studies.

4.2 REGISTRATION PROCEDURES

4.2.1 Registration at the CCR

Authorized staff must register an eligible candidate with NCI Central Registration Office (CRO) within 24 hours of signing consent. A registration Eligibility Checklist from the web site (<http://home.ccr.cancer.gov/intra/eligibility/welcome.htm>) must be completed and sent via encrypted email to: NCI Central Registration Office [contact].

After confirmation of eligibility at Central Registration Office, CRO staff will call pharmacy to advise them of the acceptance of the patient on the protocol prior to the release of any investigational agents. Verification of Registration will be forwarded electronically via e-mail to the research team. A recorder is available during non-working hours.

4.2.2 Participating Site Registration

Registration will be a two part process as patients are screened on this protocol. A protocol registration form will be supplied by the CCR study coordinator and updates will be provided as needed. Subject eligibility and demographic information is required for registration. To initially register a subject, after the participant has signed consent, complete the top portion of the form and send to CCR study coordinator. Once eligibility is confirmed, after completion of screening studies, complete the remainder of the form which is the eligibility checklist, indicating that the patient is being registered for treatment and send to CCR study coordinator. In addition, source documents supporting the eligibility criteria must be sent to the CCR study coordinator. The CCR study coordinator will notify you either by e-mail or fax that the protocol registration form has been received which will include the unique patient/subject ID number. Questions about eligibility should be directed to the CCR study coordinator or PI. Questions related to registration should be directed to the CCR study coordinator.

Subjects that do not meet screening criteria should be removed from the study following the procedure in section [5.8.3](#).

4.3 RANDOMIZATION PROCEDURES

There are two arms to this study and subjects will be randomized equally to either the TICE BCG arm or the combination arm of TICE BCG + PANVAC™. The study arms are described in detail below in Section [5.1](#). The arms will be stratified during randomization for TICE BCG

subgroup based on number of previous induction courses and time of recurrence. This is described in more detail along with the statistical analysis in the statistical section (Section 14).

5 TREATMENT PLAN

5.1 STUDY DESIGN

This is a phase II study in subjects with non-muscle invasive (stages Ta, T1, and/or CIS) high grade urothelial carcinoma of the bladder who have failed at least one course of intravesical BCG. The study will be halted for 28 days after the first six patients with combination therapy are accrued and successfully treated. If any Grade 3 or greater toxicities are observed that do not resolve with conservative management, then they will be discussed with CTEP. With preliminary evidence of safety, the remaining subjects will be accrued to the trial. (See **SCHEMA**)

- 5.1.1 All subjects will receive BCG (TICE strain, 50 mg) intravesically as per usual standard of care once weekly (+/- 2 days) starting in week 3 for a total of 6 weeks (last dose in week 8).
- 5.1.2 Subjects in the combination arm will receive the pox viral vaccines that contain the transgenes for CEA and MUC-1 (both with modified HLA-A2 agonist epitopes) as well as 3 human T-cell costimulatory molecules, B7-1, ICAM-1, and LFA-3 [rV-PANVAC™ (vaccinia) and rF-PANVAC™ (fowlpox)] as follows:
 - 5.1.2.1 rV-PANVAC™ 2 x 10⁸ pfu SQ at week 0 (+/- 7 days) only.
 - 5.1.2.2 rF-PANVAC™ 1 x 10⁹ pfu SQ at weeks (+/- 7 days) 3, 7, 11, and 15.
- 5.1.3 All subjects will provide blood, urine, and tissue (if available) at study entry and at the end of the study. Tissue at study entry can be obtained either from outside FFPE or from previous TURBT performed at NIH (see section 3.4.4.1). This tissue is required for diagnosis. All subjects will also have blood drawn at weeks 3 and 8 to coincide with the start and end of BCG treatment. Urine samples will also be obtained before and after the 1st and 3rd instillation of BCG as defined in Section 10.1.2.
- 5.1.4 All subjects will undergo tuberculin skin testing using purified protein derivative (PPD) at study entry (prior to receiving BCG instillation #1) and around the time of the week 17-20 cystoscopy/EUA. The associated skin reaction will be evaluated by a health care provider within 48-72 hours after injection. Skin induration greater than 10mm in diameter will be considered a positive result. Initial PPD results do NOT preclude subsequent treatment with BCG – these results will only be used to assess the immunologic response to BCG (see section 10.1.1).
- 5.1.5 Between weeks 17-20 (+/- 7 days), a CT urogram and chest x-ray for re-staging purposes prior to biopsy, a planned cystoscopy, exam under anesthesia, and biopsy of the previous tumor area and/or any new areas of tumor to evaluate for the presence/recurrence of disease.

5.1.6 After the initial 20 week study course, subjects will be followed for up to 1 year at the study center every 3 months per routine standard of care for high grade urothelial cancer of the bladder with cystoscopy and cytology. If recurrence is noted, it will be treated and if confirmed to be a recurrence on pathology, the patient will come off study. Surveillance and/or treatment for recurrences beyond the initial 12 months may be performed by outside urologists.

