1.2 SECONDARY OBJECTIVES

1.2.1 To estimate tumor upgrading and tumor upstaging rates for each study arm.
1.2.2 To determine the safety of the combination therapy.

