3 PATIENT SELECTION

3.1 ELIGIBILITY CRITERIA

3.1.1 Inclusion Criteria

- 3.1.1.1 Patients must have histologically confirmed localized high grade (G3) transitional cell carcinoma (urothelial carcinoma) of the bladder that is stage Ta, T1, and/or CIS

confirmed by the Laboratory of Pathology, NCI 90 days prior to study entry. This can be obtained at an outside hospital prior to entry into the study or at the NCI. However, all outside pathology specimens will require that the formalin-fixed paraffin embedded tissues be re-read by the Laboratory of Pathology, NCI. For patients enrolled at collaborating trial sites, diagnosis must be confirmed by the Department of Pathology at the institution where the patient is enrolled on the trial. Pathology can also be reviewed by the Laboratory of Pathology at the NCI if the participating trial site prefers another pathologic evaluation.

- 3.1.1.2 Patients have failed at least one previous induction course of intravesical BCG, defined as histologically confirmed persistent or relapsing tumor present on post-BCG endoscopic evaluation. All BCG failures will be considered for inclusion into the study, including BCG-refractory, -resistant, and -relapsing, as defined in the “Rationale and Background.” For the purposes of the study, “BCG-refractory” and “BCG-resistant” subjects will be considered to have “BCG-persistent” disease.
- 3.1.1.3 Patients who are not currently candidates for radical cystectomy (e.g. patient refuses surgery, comorbidities preclude major surgery, etc.).
- 3.1.1.4 Age ≥ 18 years.

Because no dosing or adverse event data are currently available on the use of BCG in combination with PANVAC™ in patients <18 years of age, children are excluded from this study.

- 3.1.1.5 ECOG performance status ≤ 2 (see Appendix A, Section 17.1).

- 3.1.1.6 Patients must have normal organ and marrow function as defined below:

- absolute neutrophil count	$\geq 1,500/\text{mcL}$
- platelets	$\geq 50,000/\text{mcL}$
- total bilirubin	$\leq 1.5 \times$ institutional upper limit of normal
- AST(SGOT)/ALT(SGPT)	$\leq 3 \times$ institutional upper limit of normal
- estimated GFR (calculated using CKD-EPI equation)	$\geq 30 \text{ mL/min}/1.73 \text{ sq.m.}$

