5.2.2.3 Between weeks 17-20 (+/- 7 days), a CT urogram and chest x-ray prior to biopsy, a planned cystoscopy, EUA, and TURBT will be done of previous tumor area and of any new areas of tumor. Tissue will be sent for pathology and be formalin-fixed paraffin embedded. If possible, some tissue will also be frozen.

- If a suspicious lesion is identified, it will be biopsied. If recurrent tumor is not found, then the subject will return every 3 months for a surveillance cystoscopy as per standard-of-care. If recurrent tumor is found, the patient has met the primary endpoint of recurrence and will be taken off study.

5.2.2.4 At every surveillance cystoscopy post-treatment up to 12 months, urine may be collected for cytology as well as for immune-related markers along with blood through 6 green top tubes for correlative immunologic aims.

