5.7 DURATION OF FOLLOW UP

Subjects will be followed for 1 year after the initial 20 week study course is completed with surveillance cystoscopy or until death, whichever occurs first.

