5.8.2 Off-Study Criteria

- Completed study follow-up period (1 year post treatment)
- Disease progression to muscle-invasive urothelial carcinoma of the bladder
- Subject's request to be taken off study. In this event, the reasons for withdrawal will be documented.
- If subjects are non-compliant with the protocol guidelines, they may be removed from the study at the discretion of the principal investigator.
- Death

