12.1.1.4 Progression-Free Survival

PFS is defined as the duration of time from start of treatment to time of progression or death, whichever occurs first. The duration of progression-free survival is measured from the start of TICE BCG therapy (week 3) until progression or death due to any cause in each study arm. Progression is defined as upstaging from a lower stage to a higher stage (e.g., Ta to T1 or T1 to T2-4; or any N+ or M+ in these high grade tumors).

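### The rule taking patients off study at first recurrence conflicts with the follow-up sections and would leave later progression unseen; the upgrading objective has no content

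*Combined protocol and SAP*

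**What the plan says.** Two sections end participation at recurrence. Section 5.1.6, on surveillance after the 20-week course, states that "if confirmed to be a recurrence on pathology, the patient will come off study". Section 5.2.2.3, on the week 17-20 evaluation, states: "If recurrent tumor is found, the patient has met the primary endpoint of recurrence and will be taken off study". That sentence stands only under the BCG-alone arm; the matching item for the combination arm, 5.2.3.6, has no equivalent.

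Two other sections do not end participation at recurrence. Section 5.7 states: "Subjects will be followed for 1 year after the initial 20 week study course is completed with surveillance cystoscopy or until death". Section 5.8.2 lists the off-study criteria; its disease-related item is "Disease progression to muscle-invasive urothelial carcinoma of the bladder", and non-muscle-invasive recurrence is not listed.

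The endpoints that depend on this are secondary. Objective 1.2.1 is "To estimate tumor upgrading and tumor upstaging rates for each study arm". Section 12.1.1.4 measures PFS from the start of BCG (week 3) to progression or death from any cause, and says: "Progression is defined as upstaging from a lower stage to a higher stage". Its examples are Ta to T1, T1 to T2-4, and any N+ or M+. Section 14.2 estimates PFS by Kaplan-Meier, reports it at 12 months with a 95% CI, and compares arms by an exploratory log-rank test. It gives no rule for a patient who leaves at a recurrence without upstaging.

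On grade, inclusion criterion 3.1.1.1 requires "histologically confirmed localized high grade (G3) transitional cell carcinoma".

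**The concern.** A site cannot follow both sets of sections. If it follows 5.1.6 and 5.2.2.3, observation stops at the event after which much progression may be expected. The Background (Section 2) hypothesises less upstaging with the vaccine, especially into the detrusor muscle, and Section 15.4 describes progression to muscle-invasive disease as something that follows multiple failed BCG courses. Those later events, and deaths, would go unrecorded.

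Kaplan-Meier treats patients censored at recurrence as having the same future progression risk as patients still free of recurrence. There is no reason to expect that. The design also assumes that more control patients recur, so the loss is unequal by arm. Because the week 17-20 removal sentence appears under one arm only, follow-up in this open-label trial could differ by arm from the first assessment.

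Upgrading is a separate matter: patients who enter at high grade (G3) cannot move to a higher grade on the scale that the protocol uses.

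**Working it through.** **Inputs from Section 14.1.** One-year RFS, BCG alone vs combination: 37.5% vs 65% (subgroup 1), 20% vs 44.7% (subgroup 2), 48% vs 65% (subgroup 3). Subgroup mix 1:5:1. Exponential RFS. 49 patients, randomized equally (Section 4.3), so 24.5 per arm on average. Accrual 1 per month for 6 months, then 2 per month, with 12 months of follow-up after accrual ends. One-sided log-rank test at 15%.

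**Step 1: the plan's own figures.** The plan gives no power or event count for progression, so the check is on the primary endpoint.

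- Expected events are the sum over patients of 1 − exp(−λ × follow-up). This gives 39.57; the plan states 40.
- A simulation of 4,000 trials gives 84.6% power for the unstratified log-rank test and 85.1% for the stratified one; the plan states 84%.

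The design rates are therefore read correctly.

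**Step 2: how many would have left.** The share with an RFS event by month m is the mix-weighted mean of 1 − S^(m/12), where S is one-year RFS.

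- 12 months, BCG alone: 1 − (0.375 + 5 × 0.20 + 0.48)/7 = 1 − 0.265 = 73.5%.
- 12 months, combination: 1 − (0.65 + 5 × 0.447 + 0.65)/7 = 1 − 0.505 = 49.5%.
- In patients: 24.5 × 0.735 = 18.0 and 24.5 × 0.495 = 12.1, about 30 of 49. The arms differ by 24 points.
- 3.5 months after BCG start, near the week 17-20 visit: about 33% and 18%.

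RFS events include death (12.1.1.3), so these are upper bounds for departure at recurrence.

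**Step 3: illustration at the planned 12 months.** These assumptions are not in the documents: subgroup 2 only, a share p = 15% of first recurrences upstaged in both arms, progression hazard h = 0.20 per year after a non-upstaged recurrence, deaths ignored. The recurrence hazards are L = −ln(0.20) = 1.609 and −ln(0.447) = 0.805 per year.

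True progression by one year = p(1 − e^(−L)) + (1 − p) × I, where I = (1 − e^(−L)) − L e^(−h)(1 − e^(−(L−h)))/(L − h).

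Kaplan-Meier with censoring at non-upstaged recurrence = 1 − e^(−pL).

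| | BCG alone | Combination | Difference |
|---|---|---|---|
| Seen at first recurrence, p(1 − e^(−L)) | 0.15 × 0.800 = 12.0% | 0.15 × 0.553 = 8.3% | 3.7 points |
| I | 0.0935 | 0.0584 | |
| True progression | 0.120 + 0.85 × 0.0935 = 19.9% | 0.083 + 0.85 × 0.0584 = 13.3% | 6.7 points |
| Kaplan-Meier as written | 1 − e^(−0.241) = 21.4% | 1 − e^(−0.121) = 11.4% | 10.1 points |

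(Differences are taken before rounding.) Censoring at recurrence makes Kaplan-Meier apply the hazard pL to patients who have left, although their assumed hazard is h. In the control arm pL = 0.241 exceeds 0.20, so progression is overstated. In the combination arm pL = 0.121 is below 0.20, so it is understated.

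**Step 4: sensitivity.** The same calculation was run on the full 1:5:1 mix, by simulation, with 10-30% of first recurrences upstaged and a 10-30% one-year progression risk afterwards (also assumed).

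- 10% upstaged, 30% afterwards: true 20.1% vs 12.8% (7.3 points); Kaplan-Meier 12.3% vs 6.6% (5.7 points).
- 30% upstaged, 10% afterwards: true 25.3% vs 17.0% (8.3 points); Kaplan-Meier 33.0% vs 18.7% (14.3 points).

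The arm difference can be understated or overstated.

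**Step 5: upgrading.** Section 3.1.1.1 admits only high-grade (G3) disease. Section 12 does not define upgrading and Section 14.2 has no analysis of it. Upstaging does have content, because entry stage may be Ta, T1 or CIS.

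**The case against.** The strongest reply is that much of the progression information survives. Recurrence is confirmed by pathology after TURBT (12.1.1.3), and a CT urogram and chest x-ray are done at weeks 17-20 (5.1.5). Upstaging up to and at first recurrence is therefore recorded and counts as a PFS event. That stands. A reader might infer that progression and upstaging cannot be estimated at all, and the documents do not support this. In the illustration, first-recurrence pathology captures 12.0 of 19.9 points of control-arm progression.

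A reader might also infer that PFS would merely repeat the recurrence comparison. That follows only if the upstaged share is constant over time and equal in both arms, and Section 2 hypothesises less upstaging with the vaccine.

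Nor is it settled that patients do leave at recurrence. Section 5.7 says otherwise and 5.8.2 omits it, although omission is weaker than contradiction. Section 14.2 states no censoring rule, so censoring at recurrence is the standard consequence of the removal rule and not something the plan prescribes.

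Finally, these endpoints are secondary and their arm comparisons exploratory. With 24.5 patients per arm, the 95% half-width for a difference near 19.9% vs 13.3% is 1.96 × √(0.199 × 0.801/24.5 + 0.133 × 0.867/24.5), about 21 points, much larger than the illustrated bias of 10.1 − 6.7 = 3.4 points. This limits the severity. It does not remove the contradiction, the difference in wording between arms, or the empty objective.

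**Conclusion.** The point holds as a conflict that should be fixed. Sections 5.1.6 and 5.2.2.3 cannot be followed together with 5.7, and recurrence is missing from 5.8.2. If the removal rule prevails, PFS and upstaging cover only events up to and at first recurrence, and the 12-month Kaplan-Meier estimate is informatively censored, with up to 73.5% vs 49.5% of patients gone by then. Those shares rest only on the plan's design rates. The illustrated bias rests on assumptions from outside the documents, and its size and direction change with them, so it should not be read as always favouring the vaccine. Upgrading in 1.2.1 cannot be answered in a G3-only population.

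A reader might fear for the primary result. RFS ends at recurrence, so it loses nothing by this rule.

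**What to change.** Reconcile 5.1.6 and 5.2.2.3 with 5.7 and 5.8.2, in identical words for both arms: a confirmed recurrence meets the primary endpoint, while stage, progression and survival continue to be collected to the end of the planned one-year follow-up. Study-calendar footnote 10 already provides for obtaining records from outside urologists when patients cannot return to the centre; extend it to patients who have recurred.

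In 14.2, state that PFS is not censored at recurrence, and report upstaging as cumulative incidence by arm with death as a competing event. Delete upgrading from 1.2.1.

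If data after recurrence cannot be obtained, redefine the endpoint as upstaging at first recurrence, with non-upstaged recurrence as a competing event.

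The cost is amendment wording plus record requests for patients who have recurred (up to about 30 of 49 by 12 months on the design rates). No new procedures are needed, and sample size and power do not change.

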5.2 TRIAL OUTLINE

5.2.1 After meeting all entry criteria based on screening evaluation, subjects will be enrolled into the study. Of note, there will be at least a 3 week delay from the time a previous bladder biopsy/TURBT to allow for adequate bladder healing prior to enrollment.

5.2.1.1 6 green top tubes of blood will be drawn for PBMCs, HLA Typing, and sera for correlative/exploratory research aims (e.g. ELISPOT, CD4+ Antigen-specific responses, etc.) on day 1 of study enrollment

5.2.1.2 Beta-HCG for women of child-bearing age (within 72 hours prior to day 1). In addition, patients, both male and female, should be willing to practice effective birth control during the study and four months following the last study treatment, unless they have had a prior hysterectomy, bilateral oophorectomy, or vasectomy.

5.2.2 TICE BCG arm:

5.2.2.1 Weeks 3-8: Receive weekly (+/- 2 days) intravesical doses of BCG (TICE strain, 50 mg) as per usual standard of care for a total of 6 weeks. Urine will be tested weekly prior to each BCG administration and the presence of gross hematuria or evidence of a urinary tract infection will result in holding that week's BCG dose and postponing therapy until the following week. Also, at the beginning of each administration, patients will be queried about urinary symptoms.

- Complaints of persistent dysuria, urgency, bladder spasms, and/or frequency from previous week's administration that is consistent with Grade 3 or greater toxicity will result in holding BCG administration for that week, supportive care (e.g. medications and hydration), and/or BCG dose reduction the following week at 1/3 normal dose as this can result in less toxicity with similar results for recurrence and progression.³¹
- Patients will be maintained at this reduced dose if they tolerate therapy.
- Future inability to tolerate this reduced dose will result in holding BCG for that week and postponing the BCG until the following week and dropping to 1/6 of the normal dose as this dose may still be effective in prolonging progression-free and cancer-specific survival times.³²

5.2.2.2 Blood and urine will be obtained for correlative studies as described in Section 10.1.

5.2.2.3 Between weeks 17-20 (+/- 7 days), a CT urogram and chest x-ray prior to biopsy, a planned cystoscopy, EUA, and TURBT will be done of previous tumor area and of any new areas of tumor. Tissue will be sent for pathology and be formalin-fixed paraffin embedded. If possible, some tissue will also be frozen.

- If a suspicious lesion is identified, it will be biopsied. If recurrent tumor is not found, then the subject will return every 3 months for a surveillance cystoscopy as per standard-of-care. If recurrent tumor is found, the patient has met the primary endpoint of recurrence and will be taken off study.

5.2.2.4 At every surveillance cystoscopy post-treatment up to 12 months, urine may be collected for cytology as well as for immune-related markers along with blood through 6 green top tubes for correlative immunologic aims.

5.2.3 TICE BCG + PANVAC™ ARM

5.2.3.1 Enroll into study with baseline evaluation and studies as described in Section 3.4. Of note, there will be at least a 3 week delay from the time a previous bladder biopsy/TURBT to allow for adequate bladder healing prior to enrollment.

5.2.3.2 Week 0 (+/- 7 days) – all subjects in this arm receive single vaccinia priming vaccine - rV-PANVAC™ 2 x 10⁸ pfu SQ after undergoing phlebotomy with 6 green top tubes for immunologic correlates.

5.2.3.3 Weeks 3-8: Receive weekly (+/- 2 days) intravesical doses of BCG (TICE strain, 50 mg) as per usual standard of care for a total of 6 weeks. Urine will be tested weekly prior to each BCG administration and the presence of gross hematuria or evidence of a urinary tract infection will result in holding that week's BCG dose and postponing therapy until the following week. Also, at the beginning of each administration, patients will be queried about urinary symptoms.

- Complaints of persistent dysuria, urgency, bladder spasms, and/or frequency from previous week's administration that is consistent with Grade 3 or greater toxicity will result in holding BCG administration for that week, supportive care (e.g. medications and hydration), and/or BCG dose reduction (BCG can be given 1/3rd of the normal dose on the following week as this can result in less toxicity with similar results for recurrence and progression³¹).
- Subjects will be maintained at this reduced dose if they tolerate therapy.
- Future inability to tolerate this reduced dose will result in holding BCG for that week and postponing the BCG until the following week and dropping to 1/6 of the normal dose as this dose may still be effective in prolonging progression-free and cancer-specific survival times.³²

5.2.3.4 PANVAC administration will continue as planned regardless of any delays in BCG administration. Research sample collection of urine will coincide with the first and third week of BCG instillation regardless of any delays with BCG administration. Research sample collection of blood will coincide with the first and sixth week of BCG instillation regardless of any delays with BCG administration. [For example, if BCG is first given on week 3 of the study, but held on week 4 and resumed on week 5, then

urine collection would be collected on weeks 0, 3, 6 (previously week 5), 18-21 (previously 17-20), and optionally on follow-up visits. In this scenario, blood would be collected on weeks 0, 3, 9 (previously week 8), 18-21 (previously 17-20), and optionally on follow-up visits. The timing of PANVAC administration will NOT change in this scenario.] Week (+/- 7 days) 3, 7, 11, and 15 – all patients in this arm receive boost fowlpox vaccines - rF-PANVACTM 1 x 10⁹ pfu SQ

- 5.2.3.5 Blood and urine will be obtained for correlative studies as described in Section 10.1.
- 5.2.3.6 Between weeks 17-20 (+/- 7 days), a CT urogram and chest x-ray prior to biopsy, a planned cystoscopy, EUA, and TURBT will be done of previous tumor area and of any new areas of tumor. Tissue will be sent for pathology and be formalin-fixed paraffin embedded. If possible, some tissue will also be frozen.
- 5.2.3.7 Also at the time of the end-of-study cystoscopy, urine will be collected for cytology and for immune-related markers along with blood for correlative aims.

